1.0 INTRODUCTION

Title	Functional Liver Imaging with Sulfur Colloid SPECT/CT in Primary and Metastatic Liver Cancer Patients Receiving Liver-Directed Treatment: A Pilot Study
Short Title	Sulfur Colloid SPECT/CT for Liver Cancers
Phase	Pilot Study
Methodology	Single Arm Open-Label
Study Duration	4 years
Study Center(s)	University of Washington Medical Center
Objectives	Study the use of SPECT/CT imaging with ^{99m} Tc sulfur colloid to characterize functional liver in patients receiving liver-directed treatments for liver cancers, and characterize liver tissue response to these treatments. The long-term goal is to use functional liver imaging to personalize liver-directed therapies in liver cancer patients by improving risk stratification and reduce treatment-related hepatotoxicity.
Number of Subjects	60 evaluable subjects
Diagnosis and Main Inclusion Criteria	Patients diagnosed with primary (hepatocellular carcinoma, cholangiocarcinoma) and metastatic liver cancers receiving liver-directed therapies (external beam radiation therapy, surgery).
Study Product, Dose, Route, Regimen	99mTc sulfur colloid SPECT/CT scans
Duration of administration	Drug administration will consist of 3 SPECT/CT scans with ^{99m} Tc sulfur colloid (one baseline scan which is standard of care, two follow-up scans which are experimental and paid for by departmental research funds).
Statistical Methodology	^{99m} Tc sulfur colloid SPECT/CT parameters will be extracted, selected, and tested for statistical association to clinical liver function status and post-treatment toxicity using a variety of statistical methodologies. Receiver-operator characteristic (ROC) analysis will determine the optimal operating point for liver function classification accuracy using SC SPECT/CT parameters. Hypothesis testing of differences between independent groups will proceed using non-parametric Wilcoxon ranksum between 2 groups or Kruskal-Wallis ANOVA between >2 groups. Hypothesis testing of differences between imaging time points of the same subjects will proceed using non-parametric Wilcoxon sign-rank or Friedman ANOVA paired comparison. Survival analysis will consist of Kaplan-Meier estimation, log rank testing, and Cox proportional hazard regression. Dose-response models will be constructed from linear and logistic regression. Prediction models will utilize robust feature selection and feature fitting through multi-fold cross validation as part of a general machine learning framework.

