4.0 STUDY DESIGN

General Design

This is a pilot study of utilizing SPECT/CT imaging with 99m Tc-SC to accurately identify and quantitate functional liver tissue on serial imaging in patients receiving RT or surgery for liver cancer. The long-term goals are to use functional imaging to improve risk stratification for selecting which patients should undergo aggressive local treatments with RT or surgery and to aid in RT planning by preferentially sparing functional liver tissue, thereby leading to reduced liver toxicity. There will be two cohorts of patients: those receiving RT (Cohort A) and those undergoing surgery (Cohort B). A total of 60 patients will be enrolled (Cohort A, n = 40; Cohort B, n = 20).

All patients will have a total of 3 SPECT/CT imaging with ^{99m}Tc-SC. The first scan in both cohorts will be routine medical care (not experimental) and will take place prior to initiation of RT or surgery. Two follow up scans will be part of the protocol. In cohort A, the first follow up scan will occur at mid-RT, and the second one about 1 month post-RT (prior to any potential anatomical liver changes). In cohort B, the first follow-up scan will occur 3-5 days postoperatively (prior to any potential liver hypertrophy), and the second one about 1 month post-operatively (when liver hypertrophy is expected to occur).

Endpoints

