4.1.2 Secondary Endpoints

Patients will receive two follow-up SC SPECT/CT scans: mid-radiation treatment (cohort A) or 3-5 days post-surgery (cohort B) and 1 month (cohort A) or 6 months (cohort B). For the second aims (a) and (b) looking at liver tissue inside the radiation field, the images will be processed similarly to the primary endpoints. Regional functional liver changes from scatter, collimator, and attenuation-corrected SPECT/CT images will be modeled as a function of regional radiation dose. Three types of dose-response models will be defined to predict changes in liver function status:

Dichotomous dose-response (complete function loss): Single dose thresholds on co-registered baseline and post-treatment SPECT/CT will be applied to investigate a binary threshold for functional loss. Image voxels exposed to a radiation dose above the selected threshold will be excluded when calculating the percent change in function liver image parameters. The product of functional liver remnant following complete loss of function on imaging (post-to-pre-treatment ratio) and baseline liver function status (e.g. ICG clearance, bilirubin, etc.) will be compared to the repeat functional liver status measured post-RT.

Binned dose-response (partial function loss): Dose threshold bins will be co-registered to the baseline and post-treatment SPECT/CT in order to explore different thresholds of radiation leading to partial loss in lung function. For imaging voxels in each dose bin, the corresponding SC SPECT/CT uptake decline will be calculated following a count normalization outside the radiation field. Model-predicted change in

SC SPECT/CT image parameters will be compared against the measured change post-therapy. The product of functional liver remnant following partial loss of function on imaging (post-to-pre-treatment ratio) and baseline liver function status (e.g. ICG clearance, bilirubin, etc.) will be compared to the repeat functional liver status measured post-RT.

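### The binned dose-response model is compared with the same pre- and post-treatment scans it was calculated from, with no held-out patients named, so agreement there is weak evidence of a dose effect

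*Combined protocol and SAP*

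**What the plan says.** Section 4.1.2 gives the models a predictive purpose: "Three types of dose-response models will be defined to predict changes in liver function status". For the binned model, "Dose threshold bins will be co-registered to the baseline and post-treatment SPECT/CT", and then "For imaging voxels in each dose bin, the corresponding SC SPECT/CT uptake decline will be calculated following a count normalization outside the radiation field". The next sentence gives the imaging check: the model-predicted change in "SC SPECT/CT image parameters will be compared against the measured change post-therapy". A further sentence multiplies the imaging remnant by baseline liver function (ICG clearance and bilirubin are the examples) and compares the product with liver function measured again after RT.

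The section does not say whether bin declines are taken per patient or pooled, how many bins there are, how pooling is weighted, or which agreement statistic is used. It reserves no patients or scans for the check. The synopsis in section 1.0 says "Dose-response models will be constructed from linear and logistic regression"; its following sentence promises multi-fold cross-validation for prediction models within a machine-learning framework. Section 4.2, as supplied, covers only the primary endpoints, and ties its protection against overfitting to the radiomics models.

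**The concern.** The bin declines are observed quantities from a pair of scans, and the measured change is a summary of that same pair. Recombining the first to predict the second asks the data to agree with themselves. How far this flatters the model depends on choices the section leaves open, but neither natural reading makes it a test of prediction.

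The stakes are modest but real. Secondary objective (b) in section 3.0 hopes to establish how much liver can be treated without materially affecting function, and section 4.0 gives sparing of functional liver in RT planning as a long-term goal. Agreement that can arise without any dose effect should not be cited in support of either.

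**Working it through.** The plan gives no figure for this comparison to reproduce, so the check is of the mechanism.

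**Inputs from the protocol.** Cohort A has n = 40 of the 60 patients (section 4.0). Each has a baseline scan and two later ones: "In cohort A, the first follow up scan will occur at mid-RT, and the second one about 1 month post-RT". Bin effects are observed declines from the baseline and post-treatment scans (section 4.1.2).

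**Assumptions, not in the protocol.** K = 4, 6 or 10 bins; random shares of liver volume per bin; SD of fractional change 0.15 between patients (range 0.05 to 0.30) and 0.10 between bins (range 0.10 to 0.15); no dose effect unless stated; 3,000 simulated trials.

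**Reading 1: declines per patient.** Let B_k and P_k be baseline and post-treatment uptake in bin k, equally normalised, with bins covering the whole region. The decline is d_k = 1 − P_k/B_k and the baseline share is w_k = B_k/ΣB. Then

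Σ w_k d_k = Σ(B_k − P_k)/ΣB = 1 − ΣP/ΣB,

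which is the measured decline, wherever the bin edges lie. The simulation gave r = 1.000 and a maximum difference of 0. The result needs an additive parameter (total or mean uptake) and the same normalisation on both sides.

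**Reading 2: declines pooled over the same patients.** If bin effects are fitted by regressing whole-liver change on bin shares, the expected null R² is (K − 1)/(n − 1): 3/39 = 0.077, 5/39 = 0.128 and 9/39 = 0.231. If instead the declines are averaged with volume weights, a patient with much liver in one bin pulls that bin's mean and gets it back with a large weight. Results with no dose effect, n = 40:

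| | 4 bins | 6 bins | 10 bins |
|---|---|---|---|
| Regression-fitted, in-sample R² | 0.08 | 0.13 | 0.23 |
| Volume-weighted pooling, in-sample R² | 0.021 | 0.025 | 0.028 |
| Volume-weighted pooling, in-sample r | 0.21 | 0.26 | 0.33 |
| Trials with r above the nominal one-sided 2.5% cut | 21% | 35% | 58% |
| Volume-weighted, leave-one-patient-out R² | −0.002 | −0.002 | −0.001 |

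Over the SD range with 6 bins, r ran from 0.19 to 0.30 and the exceedance from 21% to 47%. With only 20 evaluable patients, r was 0.29, 0.35 and 0.45. Pooling with equal patient weights nearly removed the optimism: r about 0.02 to 0.03, with 3% to 5% of trials above the cut.

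**Does the in-sample check separate dose from no dose?** With 6 bins and a decline rising from 0 in the lowest bin to 0.30 in the highest, volume-weighted r was 0.24, against 0.26 with no effect. In-sample R² rose from 0.025 to 0.059. Leave-one-patient-out R² moved from −0.002 to 0.034.

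**Choice of held-out measure.** The R² in the last table row is relative to the mean of the other patients. For 6 regression-fitted bins, leave-one-patient-out R² is about −0.22 against the mean of all 40; on that scale, simply predicting the mean of the other 39 scores 1 − (40/39)² = −0.05. Both show no predictive value under the null. Leave-one-out correlation is itself biased to about −0.5 under the null, so R² or prediction error is the better measure.

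**The case against.** The strongest reply has four parts.

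- **The identity is narrow.** The section compares image parameters processed much as for the primary endpoints. Section 4.1.1 lists liver-to-spleen ratios, a threshold-segmented functional liver volume and their product. A thresholded volume is not additive, and a spleen denominator differs from a normalisation outside the field. In a toy null simulation with per-patient bins (independent voxels, spleen-change SD 0.15, voxel-noise SD 0.05 to 0.30), r was only about 0.04 to 0.08 for the thresholded volume and −0.03 to 0.03 for the ratio. This stands: a reader might infer that agreement is guaranteed or that the check cannot fail, and the protocol does not support that in general.
- **The objectives have other evidence.** The gradient of decline across bins, the voxel-level linear and logistic regression, and the comparison with repeat clinical function all bear on them. This also stands, so it would be wrong to infer that secondary objectives (a) and (b) are left without evidence. Baseline function does enter the predicted value in the clinical comparison and may by itself correlate with the repeat value.
- **Cross-validation may already apply.** The synopsis promises it for prediction models, and these models are meant to predict. The coverage is ambiguous rather than absent. But the synopsis describes dose-response models in a separate sentence, and no fold unit is given; folds of voxels or bins within a patient need not remove the optimism.
- **The pooled optimism is small and no test is specified.** An R² of 0.02 to 0.03 would persuade nobody, and the exceedance rates above matter only if someone tests the correlation. This is fair, and it limits the size of the point without making the comparison informative.

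**Conclusion.** The concern holds in limited form. As written, the imaging check of the binned model is an identity (patient-specific declines, additive uptake, common normalisation) or an in-sample fit (pooled declines). By itself it gives little evidence that dose predicts functional loss.

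The size depends on the method left open: exact agreement in the first case; null R² of about 0.08 to 0.23 with regression-fitted bins; R² of 0.02 to 0.03 with r of 0.21 to 0.33 under volume-weighted pooling; almost no optimism with equal patient weights. These figures rest on n = 40 and on assumed bin numbers, shares and SDs. That the check is in-sample is read from the absence of any named held-out data.

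This is a secondary, exploratory analysis in a pilot study, and no sample size or error rate depends on it. It is worth correcting because a better comparison is available from the same data.

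**What to change.** In section 4.1.2, for the binned model:

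1. State whether declines are per patient or pooled, and how pooling is weighted.
2. Fix the dose bins in advance, or choose them inside the training folds.
3. Estimate the bin declines with the index patient left out, meaning all of that patient's voxels and scans.
4. Apply them to that patient's baseline image and dose map, and compare the prediction with that patient's measured change.
5. Report held-out prediction error or R² against a no-dose model: one common decline estimated from the other patients.

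Add one sentence to the synopsis or to section 4.2 saying that cross-validation is by patient and applies to any dose threshold or dose-response curve used as a predictor.

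The cost is a leave-one-patient-out loop on data already planned, with no new patients, scans or staff. The reported fit will be lower than the in-sample figure.

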3.0 STUDY OBJECTIVES

3.1 Primary Objectives

- a) Develop new quantitative metrics of baseline SC uptake on SPECT/CT imaging and correlate with clinical parameters of liver function and clinical outcomes in liver cancer patients receiving RT or surgery.
 - Hypothesis: Global metrics of baseline pre-treatment SC uptake on SPECT/CT imaging are more predictive for survival than conventional clinical measures of liver function and are associated with ICG clearance. For patients receiving surgery, the volume of the future liver remnant (FLR) as defined by SC SPECT/CT imaging (functional FLR) is more predictive for PHLF than CT-defined FLR volumes. Heterogeneity metrics of baseline SC uptake are associated with the severity of cirrhosis and prior liver-directed therapy; specifically, SC uptake within the liver is more heterogeneous in less compensated livers and in those that have received a higher number of liver-directed therapies.
- b) Correlate *post-treatment* changes in SC uptake on SPECT/CT imaging with changes clinical liver function.

Hypothesis: Changes in SC uptake between pre-RT and mid-RT/post-RT SPECT/CT scans are associated with changes in clinical liver function in response to RT and are predictive of liver toxicity at earlier time points compared to clinical assessments of liver function. SC uptake in the FLR (non-treated) is stable and preserved over time between pre-surgery and immediately post-surgery (3-5 days postoperative) scans.

Secondary Objectives

- a) Estimate the dose response relationship on multiple spatial scales (global liver, regional liver, liver image voxel) between radiation dose and changes in SC uptake, both acutely (mid-RT) and subacutely (1 month post-RT), using SC SPECT/CT imaging.
 - Hypothesis: Deficits in SC uptake due to absorbed dose is governed by a linear dose relationship. As the dose delivered to the region/voxel increases, the uptake in SC decreases in a linear fashion.
- b) Estimate the degree of radiation response in liver tissue with varying levels of function (i.e. compare radiation dose response of well compensated livers against less compensated livers).

This may establish a threshold of liver tissue that would be "safe" to treat without significantly affecting liver function.

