Hypothesis: Varying degrees of cirrhosis have different radiation dose response curves; specifically, more cirrhotic livers have a lower threshold for injury (more radiosensitive) than less cirrhotic or non-cirrhotic livers. The dose-response relationship can be modeled either as a linear or sigmoid function.

c) Correlate SC uptake on SPECT/CT imaging in FLR with extent of liver hypertrophy after surgical resection.

Hypothesis: In patients undergoing surgery, the functional FLR is predictive of the adequacy of the FLR and the extent of liver hypertrophy after hepatectomy. Higher functional FLR decreases the risk of PHLF and has a higher capacity and ability to hypertrophy compared to less functional FLR.

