Continuous dose-response (function loss distribution): The continuous dose distribution will be coregistered to the baseline and post-treatment SPECT/CT. The relationship between dose and SC SPECT/CT uptake reduction at the voxel scale will be directly characterized via linear and logistic regression methods with noise suppressing fitting techniques (multiscale lung \rightarrow lobar \rightarrow voxel model). Goodness of model fits (pseudo R^2) using rigid and deformable registration of SPECT/CT images and RT dose will be compared. The product of functional liver remnant from the function loss distribution on imaging (post-to-pre-treatment ratio) and baseline liver function status (e.g. ICG clearance, bilirubin, etc.) will be compared to the repeat functional liver status measured post-RT.

Statistical Analysis

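### The voxel-scale dose-response regression names no patient-level term, although it serves a between-patient comparison with at most 40 independent units

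*Combined protocol and SAP*

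**What the plan says.** The continuous dose-response paragraph of section 4.1.2 states: "The relationship between dose and SC SPECT/CT uptake reduction at the voxel scale will be directly characterized via linear and logistic regression methods". The synopsis in section 1.0 agrees: "Dose-response models will be constructed from linear and logistic regression". Secondary objective (a) in section 3.0 sets the scales: "Estimate the dose response relationship on multiple spatial scales (global liver, regional liver, liver image voxel".

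Secondary objective (b) is to "compare radiation dose response of well compensated livers against less compensated livers", under the hypothesis that "Varying degrees of cirrhosis have different radiation dose response curves". Section 4.1.2 ties both aims to its three dose-response models with the words "For the second aims (a) and (b) looking at liver tissue inside the radiation field".

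The only hierarchy mentioned is spatial. The regression is to be done "with noise suppressing fitting techniques (multiscale lung", then lobe, then voxel (the text says lung in a liver study). It has no patient level. Two outputs are named for the voxel model. One is a fit statistic: "Goodness of model fits (pseudo R^2) using rigid and deformable registration of SPECT/CT images and RT dose will be compared". The other sets a predicted liver function, formed from the imaging ratio and the baseline value, against the function measured after RT.

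The Statistical Analysis heading contains only 4.2.1 Primary Endpoints, so no later text describes inference for the secondary aims. Within-subject dependence is addressed only in the synopsis, and only for repeated imaging time points.

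**The concern.** Linear and logistic regression, used in the ordinary way, treat each row of data as independent. Voxels from one liver share that patient's radiosensitivity, prior treatment and scan conditions, and neighbouring voxels are likely to be correlated as well. Degree of cirrhosis is essentially a property of the patient. A comparison of curves by cirrhosis therefore gains precision mainly from more patients, and very little from more voxels in the same patients.

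If all voxels were placed in one regression, the dose-by-cirrhosis contrast could appear significant when the groups do not differ, and intervals around dose-response parameters could be too narrow. Objective (b) hopes the comparison may indicate which liver tissue can be treated without materially harming function, so false precision there would matter.

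**Working it through.** **No figure to reproduce.** The documents give no power calculation, significance level, intraclass correlation, slope variance or voxel count. The check asks what happens if voxels are pooled and conventional errors are used.

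**Input from the documents:** 40 RT patients (section 4.0).

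**Assumed inputs:**
- two cirrhosis groups of 20 with no true difference;
- dose D uniform on 0–60 Gy within each patient, so Var(D) = 60²/12 = 300;
- mean slope −0.5 percentage points of uptake per Gy;
- between-patient intercept SD 5 and voxel residual SD 20, so σ² = 5² + 20² = 425;
- between-patient slope SD τ of 0, 0.05, 0.1 or 0.2, that is a CV of 0, 10, 20 or 40% of the mean slope;
- m = 200, 1000 or 5000 voxels per patient;
- two-sided 5% test;
- no spatial correlation.

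**Simulation** (1000 replicates; 300 at m = 5000). Naive means pooled least squares. Patient-level means one slope per patient, then a t-test between groups.

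| m | τ | true SE / naive SE of slope | naive type I error | patient-level type I error |
|---|---|---|---|---|
| 200 | 0 | 1.01 | 5.4% | 5.1% |
| 200 | 0.05 | 1.15 | 9.2% | 5.2% |
| 200 | 0.1 | 1.49 | 19.4% | 4.3% |
| 200 | 0.2 | 2.42 | 45.0% | 5.3% |
| 1000 | 0 | 1.04 | 6.5% | 6.7% |
| 1000 | 0.05 | 1.63 | 23.4% | 4.9% |
| 1000 | 0.1 | 2.78 | 50.2% | 4.2% |
| 1000 | 0.2 | 5.33 | 71.2% | 4.5% |
| 5000 | 0 | 1.06 | 5.7% | 5.3% |
| 5000 | 0.05 | 3.07 | 52.7% | 5.0% |
| 5000 | 0.1 | 6.15 | 71.3% | 4.7% |
| 5000 | 0.2 | 11.75 | 86.7% | 6.3% |

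The type I errors are for the difference in slope between cirrhosis groups. Coverage of the 95% interval for the mean slope was 92–97% at patient level. For the naive analysis it fell from 94% to 12%.

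**Closed-form check.** The naive variance of the pooled slope is about σ²/(40·m·300), and the true variance adds τ²/40. Hence ratio ≈ √(1 + m·300·τ²/425).
- m = 200, τ = 0.05: √(1 + 0.353) = 1.16 (simulated 1.15).
- m = 1000, τ = 0.1: √(1 + 7.06) = 2.84 (simulated 2.78).
- m = 5000, τ = 0.2: √(1 + 141.2) = 11.9 (simulated 11.75).

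Setting τ = 0 gives a ratio of 1. Shared intercepts alone do not distort a within-patient dose slope. Slope variation between patients does, and so would spatial correlation.

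**Other assumed inputs.** Dose uniform on 0–50 Gy, mean slope 1% per Gy, voxel noise SD 0.30, slope CV 20–40% and 200–1000 voxels give a naive type I error of 27–79% and an SE ratio of 1.7–5.8. The patient-level error is 3–5%.

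**Group means instead of slopes.** If mean uptake change were compared between groups on pooled voxels, the design effect 1 + (m − 1)·ICC applies. At m = 1000 and an assumed ICC of 0.01, it is 1 + 999 × 0.01 = 11.0. The SE is then understated √11.0 = 3.3-fold, and the type I error is 2Φ(−1.96/3.3) = 55%.

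**The case against.** The strongest reply is that the plan never says what this calculation supposes. It does not say that voxels are pooled across patients, and it specifies no standard error, interval or p-value for the voxel slope. One of its two named outputs, the comparison with measured liver function, uses whole-patient quantities. The synopsis also gives a general rule for independent groups: rank-sum for two, Kruskal-Wallis for more. Applied to one slope per patient, that rule is close to the two-stage analysis recommended here. The aims are secondary, worded as estimation, and belong to a pilot.

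Most of this stands. The gap is an omission, not a declared decision to treat voxels as independent. A reader might infer that the reported standard errors are bound to be much too small, but the documents do not support that, because the analysis that would produce them is not specified.

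The reply does not close the gap. No text says that the rank-sum rule will be applied to per-patient slopes. The methods that are named assume independence when used conventionally. Comparing curves between groups needs some statement of uncertainty, and the plan does not say on what unit it will rest.

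**Conclusion.** The point holds as a conditional one. The voxel-scale analysis has no patient-level term while serving a comparison with at most 40 independent units. If voxels are pooled with conventional errors, the inference is anti-conservative. Under the assumptions shown, the standard error ratio runs from about 1 to more than 10 and naive type I error from about 5% to over 80%.

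The harmless end requires no slope variation between patients and no spatial correlation. Some slope variation is likely: sections 5.1.1 and 5.1.4 admit primary and metastatic tumours, leave prior treatment unrestricted and allow concurrent chemotherapy, and section 7.0 covers 5- and 15-fraction regimens. Its amount is unknown.

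Two further inferences are tempting and unsupported. A reader might take objective (b) to promise a safe dose threshold; its text refers to a threshold of liver tissue, and only as a possibility. A reader might also argue that a real liver has so many voxels that the inflation must exceed these figures. The imaging protocol gives no voxel size or count, and more voxels raise the ratio only if slopes vary or voxels are spatially correlated. The primary analyses are unaffected.

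**What to change.** In section 4.1.2, replace plain voxel regression with one of two patient-level analyses:
- a mixed-effects dose-response model with a random intercept and random dose slope per patient, and cirrhosis or liver-function group as a patient-level covariate that interacts with dose; or
- a separate fit for each patient, followed by a comparison of the patient slopes between groups.

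Take confidence intervals for the dose-response parameters, and for any threshold derived from them, from a bootstrap that resamples patients. Because whole livers are resampled, this also carries the spatial correlation within each liver. State that n for the comparison by liver function is the number of patients.

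The cost is slightly more analysis work and wider confidence intervals. No new scans, visits or patients are needed.
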